6.2.3 Inclusion of Women and Minorities

Both men and women of all races and ethnic groups are eligible for this trial.

6.3 Location of study

Patient will be seen and evaluated at the NIH Clinical Center inpatient unit or outpatient clinic according to the study calendar.

6.4 Description of recruitment strategies

Most often, patients call the Principal Investigator at the suggestion of the ECD Global Alliance, a family-patient organization that has its own web site and contact information. In addition, the medical community knows of the Principal Investigator's interest in ECD, and refers patients. Patients with the pathologic findings of ECD and BRAFV600E mutation are immediately accepted for possible enrollment. See figure 1 on section 6.2.1 for a flowchart explaining the recruitment strategies.

6.5 For existing sample/data sets, note whether samples were originally collected for research or clinical practice. If obtained for research, include a description of the original purpose of study and prior plans for sample storage. Was consent obtained that would be applicable to this study?

Patients enrolled on NHGRI Protocol 11-HG-0207 are potential candidates for this trial as long as the BRAF mutations V600E or V600K were detected in their samples. These samples were collected for clinical diagnostic as well as research purposes and consent was obtained at moment of enrollment to the natural history study. The clinical use of these samples was to confirm the pathological diagnosis of ECD. These samples were then analyzed under research for BRAF mutation testing which was then CLIA certified. Patients that will be considered as enrollees to this trial, but are unknown to our natural history study, will be enrolled on study 11-HG-0207 and tissue will be collected for confirmation of BRAF status prior to enrollment into this clinical trial. The 11-HG-0207 patient subject consent form is attached as Appendix 3.

6.6 Description of any financial compensation. If participant withdraws early, describe whether compensation will be modified.

NA.

7.0 Description of study statistical considerations and/or analytic plan:

7.1- STATISTICAL CONSIDERATIONS

7.1.1- Study Design/Endpoints

Patients with BRAFV600E positive Erdheim Chester disease will be enrolled in this study and will be evaluated at the NIH Clinical Center in Bethesda, Maryland. Patients will be referred to this trial from NHGRI protocol 11-HG-0207, which performs clinical and basic investigations into Erdheim Chester disease. Referrals will also be accepted from treating physicians, the ECD Global Alliance and patients themselves. Patient will be admitted for 4-5 days at the NIH Clinical Center and baseline testing will be performed prior to the first dose administration. Patients without progression or significant AEs may continue therapy for a maximum of 12 months. At six months, patients without RECIST- defined response or major clinical improvement may elect to discontinue therapy. There will be no randomization due to the rarity of the disease and small patient population. Patients will be seen once at the start of their participation in the trial, and again 1 week, 1 month, 2 months, 4 months, and 6 months, 8 months, 10 months and 12 months after the initial admission. At 12 months, therapy will be stopped and follow up will be for one year after completion of therapy at 15 months, 18 months and 24 months, but for proper analysis of treatment response and other variants, follow up could be prolonged. It is our intention to recruit at least 18 patients within approximately one year. In addition, we have access to approximately 100 cases in the USA and worldwide through the ECD Global Alliance. No placebo will be used and patients must stop their current ECD treatment at least 4 weeks before enrollment; this applies to cases in which the patient is not responding to current treatment.

To determine the clinical response rate, baseline measurable disease, as per RECIST 1.1 criteria, will be determined less than 4 weeks prior to the start of treatment or at the baseline visit. Patients with ECD must have measurable or evaluable disease in one or more systems. These can include, but are not limited to, the retro-orbital space, pituitary stalk, cerebellum, brainstem, heart, retroperitoneal space causing renal and aortic encasement and long bones of upper and lower extremities. Complete response can be determined through imaging studies of these areas. As described in the treatment plan, imaging studies will be performed including retro-orbital/pituitary/brain/cerebellar MRI, abdomen and pelvis CT, and cardiac CT and MRI. FDG PET scan and T-99m bone scan will also be performed as exploratory outcome measures. The required imaging study will be selected on a case-by-case basis since the disease is heterogeneous in its presentation. Response to therapy will be evident on follow up imaging studies revealing a decrease in lesion size of 30% or more, which is defined as a partial response as per RECIST Criteria, when compared to baseline studies. After 12 months of therapy have been completed, patients will go to an off therapy follow up period that will have follow up visits at 15 months, 18 months and 24 months. During this period, duration of response will be assessed through

imaging studies of the patient's target lesions. If these target lesions show an increase, in at least one diameter, of 20% or more when compared to that target lesion measurement when they completed 12 months of therapy, this will be considered recurrence/progression of disease. Patients with disease recurrence will be considered for therapy resumption at the dose they were on when they completed therapy. Patients considered for therapy resumption will need to meet all inclusion and exclusion criteria and have new registration and TAC. They will also follow the safety guidelines for toxicity and dose modifications.

Besides imaging follow up, duration of response will be also assessed through patient's report of symptoms according to the MD Anderson symptom inventory, quality of life measures and SUV values on PET scan. Cytokines will also be followed during this period. All these parameters will help us determine disease recurrence-progression on each case.

The study will be conducted as an optimal Simon two-stage phase II trial in order to rule out an unacceptably low 10% clinical response rate (PR+CR: $p_0=0.10$) in favor of a targeted rate consistent with 40% ($p_1=0.40$). Maximum trial size would be set at 18 evaluable patients. If at least 4 responses (at least 22%) were observed among the 18 evaluable patients, this regimen would be considered worthy of further testing in this disease. If no responses were observed among the initial 6 patients, the study would be terminated early and declared negative. This design yields at least 90% power to detect a true response rate of at least 40%. It yields at least .90 probability of a negative result if the true response rate is no more than 10%, with at least .59 probability of early negative stopping. A temporary pause in the accrual to the trial may be necessary to ensure that enrollment to the second stage is warranted.

To ensure safety and feasibility of the selected dose for patients with ECD, we will assess the toxicity profile and dose delivery after the first 6 subjects have completed 3 months of therapy. If 3 or more individuals do not take at least 80% of the full doses of both drugs over 3 months due to dose modification for toxicity, revision of the dose schedule should be considered. Safety will be monitored on a continuous basis and feasibility of drug administration will be reviewed after 12 patients and then 18 patients have completed the 3 months of therapy.

All patients who receive any amount of the study drug will be evaluable for toxicity. Toxicity and doses adjustment will be perform as per the guidelines discussed on sessions 4.7 and 9 where dosing modifications and adverse events are discussed. Reassessment of the dose-schedule when 3 months or 12 cycles of therapy are completed will be performed by collecting the patient's medication diary information. This information will be collected by the study PI or the study coordinator by direct communication with the patient.

Besides response measured through imaging studies, physical and emotional well-being will be evaluated to assess improvement in daily living as exploratory endpoints. These

evaluations will be performed by the rehabilitation medicine and pain and palliative care teams during the treatment part of this trial as well as the off therapy follow up period. The list of tools and evaluations is available on sections 4.1.2 and 11.3.

7.1.2- Stratification Factors

N/A

7.1.3- Analysis of Secondary Endpoints

As secondary evaluations, time to response, duration of response, PFS and OS will be reported separately using Kaplan-Meier curves and appropriate 95% confidence intervals. Every report will contain all patients included in the study. These findings will be compared informally to other similar published results in patients with the same disease.

Other exploratory analyses will include FDG-PET, CT, bone scans, and levels of C-reactive protein, ESR, and cytokines. There are no specific ECD biomarkers that can be measured in blood, urine or tissue in order to assess disease activity.

In patients affected by central nervous system disease (mainly cerebellar and brain stem disease), improvement in overall physical function and conditioning will be assessed. Patients will be evaluated by rehabilitation medicine and neurology. Improvement of their overall quality of life will be evidence of response, and assessments will be made at baseline and throughout the trial, as well as at the conclusion of the trial, to evaluate for any improvement in quality of life.

Resistance to therapy will be evaluated through imaging studies and patient follow up for at least one year, but this is not expected with the combination therapy.

7.1.4- Reporting and Exclusions

Evaluation of Toxicity

All patients will be evaluable for toxicity from the time of their first treatment with Dabrafenib mesylate (GSK2118436B, NSC 763760) and Trametinib dimethyl sulfoxide (GSK1120212B) (NSC 763093).

CTEP is the sponsor of the trial. The principal investigator and study data manager will monitor the safety data. CTEP will be notified of serious adverse events as soon as the PI, associate investigator or study data manager are aware of them through the expedited reporting systems and all AEs through the routine reporting to CDS. The National Human Genome Research Institute Intramural Data Safety and Monitoring Board (DSMB) will also monitor this trial. Monitoring by the DSMB will include receipt of quarterly updates regarding the trial status and accrual with a report every 6 months summarizing safety data as provided by the investigational staff. The DSMB will follow the protocols stopping

guidelines for serious adverse event as described in sections 4.7 and 9. Timing of the reports may be adjusted based on the rate of enrollment or any other circumstance that might warrant increased monitoring, for example if more than expected adverse events are reported on the quarterly updates, safety data reports may be available sooner than 6 months.

The NHGRI DSMB is led by [name], executive secretary, NHGRI DSMB. Other DSMB members include physicians and ethicists. Three members of the DSMB are from outside NIH and one is from within the NIH.

Evaluation of Response

All patients included in the study must be assessed for response to treatment, even if there are major protocol treatment deviations or if they are ineligible. Each patient will be assigned one of the following categories: 1) complete response, 2) partial response, 3) stable disease, 4) progressive disease, 5) early death from malignant disease, 6) early death from toxicity, 7) early death because of other cause, or 9) unknown (not assessable, insufficient data). [Note: By arbitrary convention, category 9 usually designates the “unknown” status of any type of data in a clinical database.]

All the patients who met the eligibility criteria (with the possible exception of those who received no study medication) will be included in the main analysis of the response rate. Patients in response categories 4-9 will be considered to have a treatment failure (disease progression). Thus, an incorrect treatment schedule or drug administration does not result in exclusion from the analysis of the response rate. Precise definitions for categories 4-9 will be protocol specific.

All conclusions will be based on all eligible patients. Subanalyses will be performed on the basis of a subset of patients, excluding those for whom major protocol deviations have been identified (*e.g.*, early death due to other reasons, early discontinuation of treatment, major protocol violations, etc.). However, these subanalyses will not serve as the basis for drawing conclusions concerning treatment efficacy, and the reasons for excluding patients from the analysis will be clearly reported. The 95% confidence intervals will also be provided.

8.0 Description of potential benefits of study:

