5.1 Diagnostic tests and procedures

Certain laboratory and imaging studies will have been performed as part of the natural history protocol for ECD. However, the studies described in this Section will be performed specifically for this treatment protocol. Baseline evaluations are to be conducted within 1 week prior to start of protocol therapy. Scans and x-rays must be done \leq 4 weeks prior to the start of therapy. In the event that the patient's condition is deteriorating, laboratory evaluations should be repeated within 48 hours prior to initiation of the next cycle of therapy. See study calendar below.

Table 4. Study Calendar

	Pre-Study	Wk 1	Wk 4	Wk 8	Wk 16	Wk 24	Wk 32	Wk 40	Wk 48	Off Therapy Wk 60	Off Therapy Wk 72	Off Therapy Wk 96
Dabrafenib mesylate (GSK2118436B) (NSC 763760)		A	A	A	A	A	A	A	A	C	C	C
Trametinib dimethyl sulfoxide (GSK1120212B) (NSC 763093)		B	B	B	B	B	B	B	B	D	D	D
Informed consent	X									Reviewed and re-consented as needed.	X	X
Demographics	X	X	X	X	X	X	X	X	X	X	X	X
Medical history	X	X	X	X	X	X	X	X	X	X	X	X
Concurrent meds	X	Throughout the study and modified as needed.										
Physical exam	X	X	X	X	X	X	X	X	X	X	X	X
Vital signs	X	X	X	X	X	X	X	X	X	X	X	X
Height	X	X	X	X	X	X	X	X	X	X	X	X
Weight and Nutrition	X	X	X	X	X	X	X	X	X	X	X	X
Performance, RPM,	X	X	X	X	X	X	X	X	X	X	X	X

Cardiology	X		X	X	X	X	X	X	X	As needed per clinical assessment	X	X
Dermatology	X		X	X	X	X	X	X	X	X	X	X
Ophthalmology	X		X	X	X	X	X	X	X	X	X	X
Neurology	X		X	X	X	X	X	X	X	X	X	X
CBC w/diff, plts	X	X	X	X	X	X	X	X	X	X	X	X
24h Urine ^a			X						X	Instead of 24 urine collections, random testing will be performed instead.	X	X
Serum chemistry ^b	X	X	X	X	X	X	X	X	X	X	X	X
Blood hematology ^c	X	X	X	X	X	X	X	X	X	X	X	X
PBMC Cytokines	X			X		X			X		X	X
EKG	X		X	X	X	X	X	X	X	X	X	X
Echocardiogram	X		X	X	X	X	X	X	X	X	X	X
MUGA										As needed		
Adverse event evaluation										Throughout the study		
RECIST 1.1 Tumor Size (MRI and CT) ^E	X			X	X	X	X	X	X	Only target lesions will be monitored at 60-72-96 wks f/u minimizing scans and radiation.	X	X
FDG-PET	X			X	X	X	X	X	X	X	X	X
Bone scan	X			X	X	X	X	X	X	X	X	X
B-HCG	X ^d		X	X	X	X	X	X	X	X	X	X

Other tests, as appropriate*	X			X	X			X		X	X	X	
Other correlative studies (Proteomics) f	X ^f	When possible											

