		
A: Dose as assigned; administration schedule for 48 weeks (12 cycles). Therapy will stop after 12 cycles and patient will be followed for 48 weeks off therapy
 
B: Dose as assigned; administration schedule for 48 weeks (12 cycles). Therapy will stop after 12 cycles and patient will be followed for 48 weeks off therapy
 
C-D: Off therapy, if PD is seen during follow up and prior to 96 weeks off therapy, therapy will be resumed at the dose level of the last cycle. Patient needs to meet all eligibility criteria once more before therapy is resumed. Duration of therapy will be discussed with the CTEP monitor.
 
E: During the off therapy follow up period, MRI and CT scans will performed based on the target lesions followed on each case. All patient will have a whole body PET-CT and bone scan performed.
 
a: Volume, creatinine, protein, glucose, phosphate, BRAF V600E DNA assay
 
b: Albumin, alkaline phosphatase, total bilirubin, bicarbonate, BUN, calcium, chloride, creatinine, glucose, LDH, phosphorus, potassium, total protein, SGOT [AST], SGPT [ALT], sodium, magnesium, GGT, cholesterol, triglycerides, HDL, LDL, uric acid
 
c: ESR, CPR, PT, PTT
 
d: Serum pregnancy test (women of childbearing potential); must be performed within 14 days of the first dose of study treatment.
 
e: Off-study evaluation.
 
f: Proteomics will be performed on biopsies of accessible tumor tissue, when available.
 
g: Dermatology evaluations will continue for 6 months after the last dose of the study agents.
 
* For some patients, testing will be customized based upon clinical manifestations. In those cases, certain of the following studies will be performed at baseline and at 2, 6 and 12 months; EMG, EEG, PFTs, NO and other clinical indicated tests.
 
+ After problem No. 6 (June 21, 2017), BRAF V600E quantification through blood and urine was removed from the study. This also applies to the Spirituality tool administered through PPC.
											

5.1.1 - Laboratory tests.

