At the initial NIH Clinical Center admission for this protocol, a baseline history and physical examination and several laboratory tests, procedures, and consultations will be performed on all patients. After all screenings are completed, each patient's information will be recorded and disease severity will be analyzed. Patients will remain on any supplements and non-ECD medications that they have been receiving, except for prohibited drugs, e.g., those listed in Section 4.3. After the start of therapy, admissions to the NIH CC will occur at 1 week, one month, 2 months, 4 months, 6 months, 8 months, 10

months and 12 months. After the completion of 12 months of therapy, patients will be followed at 15 months, 18 months and 24 months in order to allow for monitoring of disease stability and recurrence off therapy. Patients can also be seen and evaluated at outpatient clinics or day hospitals during follow up visits.

Testing will be individualized based upon clinical findings, but certain studies will be performed on every patient.

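### The off-therapy recurrence rule behind duration of response is set per lesion, with no sum of diameters and no absolute minimum, and is not reconciled with the RECIST wording elsewhere in the protocol

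*Combined protocol and SAP*

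**What the plan says.** Section 7.1.1 says that duration of response off therapy is followed by imaging of the target lesions at months 15, 18 and 24. Recurrence or progression is called as follows: "If these target lesions show an increase, in at least one diameter, of 20% or more when compared to that target lesion measurement" at completion of 12 months of therapy. The same section adds that "Patients with disease recurrence will be considered for therapy resumption", and that symptoms, quality of life, SUV and cytokines are also followed: "All these parameters will help us determine disease recurrence-progression on each case". None of these has a threshold.

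Other places describe the same visits differently:
- Section 5.1.2 says that the imaging outcome measures are assessed by RECIST criteria at every scheduled admission except week 1.
- The Table 4 row headed "RECIST 1.1 Tumor Size (MRI and CT") runs through weeks 60, 72 and 96.
- Table 4 note C-D has therapy resumed "if PD is seen during follow up and prior to 96 weeks off therapy", without defining PD.

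Section 6.2.1 accepts lesions of 10 mm by spiral CT, MRI or calipers. Section 7.1.3 reports duration of response, PFS and OS by Kaplan-Meier with 95% confidence intervals, and compares them informally with published results.

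**The concern.** The rule has three gaps.
- It works lesion by lesion, so one lesion can trigger recurrence while the total burden falls.
- It has no absolute minimum, so for a small lesion the trigger is a change of one or two millimetres.
- Its grammar mixes a plural (the lesions) with a singular (that lesion's measurement), so any-lesion and all-lesions readings are both possible. The any-lesion reading is the more natural.

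If the sections on RECIST are meant to govern, the 7.1.1 rule conflicts with them, and nothing says which prevails.

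At stake is the duration-of-response curve just after the planned stop of therapy. Section 5.1.1 schedules these visits "in order to allow for monitoring of disease stability and recurrence off therapy". That purpose makes month 12 a reasonable reference, and it is not criticised here. PFS is affected only if it uses the same event; Section 7.1.3 does not define one.

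**Working it through.** The plan states no figure to reproduce, so the check applies its thresholds directly and then asks how often reading error alone would meet them.

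**1. Direct arithmetic (document values only).** Smallest measurable lesion 10 mm (6.2.1); partial response is a fall of 30% or more (7.1.1); recurrence is a rise of 20% or more (7.1.1).
- 10 × 0.70 = 7.0 mm. Then 7.0 × 0.20 = 1.4 mm, so recurrence is called at 8.4 mm, still 16% below baseline.
- Month-12 values of 10 and 40 mm becoming 12 and 30 mm: the first lesion is up 20%, so recurrence is called. The sum changes by (12+30)/(10+40) − 1 = −16%.

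**2. False calls with no true growth.** Assumptions, none of them in the documents: independent log-normal reading error with SD 5, 7 or 10%, no change in true size, scans at months 15, 18 and 24. For one lesion at one visit, P = 1 − Φ(ln 1.2 / (SD × √2)) = 0.50 / 3.3 / 9.9%. The three visits share one month-12 reading, so the three-visit rate was simulated (400,000 patients per cell):

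| Rule | Lesions | SD 5% | SD 7% | SD 10% |
|---|---|---|---|---|
| Any lesion up 20% | 1 | 1.4% | 8.0% | 22% |
| | 2 | 2.7% | 15.5% | 38% |
| | 3 | 4.0% | 22% | 52% |
| All lesions up 20% | 2 | 0.01% | 0.3% | 2.6% |
| | 3 | 0.00% | 0.01% | 0.3% |
| Sum up 20% and 5 mm | 1 × 20 mm | 0.07% | 1.7% | 10% |
| | 2 × 20 mm | 0.04% | 1.3% | 8.4% |
| | 3 × 20 mm | 0.00% | 0.2% | 3.4% |
| | 10 + 40 mm | 0.3% | 3.3% | 14% |
| | 1 × 40 mm | 1.4% | 8.1% | 22% |

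The 5 mm is only an illustration. It does nothing for a single 40 mm lesion, where 20% is already 8 mm.

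**3. In patients.** Section 7.1.1 tests against a 10% response rate "in favor of a targeted rate consistent with 40" per cent, with 18 evaluable patients: 0.40 × 18 = 7.2 responders. Any-lesion reading, at SD 5 / 7 / 10%:
- one lesion: 0.10 / 0.58 / 1.55 patients
- three lesions: 0.29 / 1.60 / 3.72 patients

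**4. Relation between the rules.** If every lesion is below 1.2 times its own month-12 value, the sum is below 1.2 times the month-12 sum. So a sum event can only remove or delay any-lesion calls. Against the all-lesions reading it can add calls (two 20 mm lesions, SD 7%: 1.3% against 0.3%).

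**5. Price in true relapse.** Assume growth of 30/60/100% at months 15/18/24 and SD 7%. Percentage called by those months if growth simply continues:

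| Growing | Any-lesion rule | Sum and 5 mm |
|---|---|---|
| One of two 20 mm | 80 / 99.9 / 100 | 27 / 88 / 99.9 |
| One of three 20 mm | 80 / 99.9 / 100 | 6.5 / 51 / 97 |
| Both of two 20 mm | 96 / 100 / 100 | 87 / 100 / 100 |
| Single 7 mm | 79 / 99.9 / 100 | 0 / 20 / 97 |

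**6. Effect of resumption.** Now assume that every any-lesion call leads to resumption and that growth then stops. If scans after resumption are still used, the sum event ever captures about 64% (one of two), 24% (one of three) and 3% (single 7 mm) of these relapses. Ignoring resumption would therefore lengthen duration of response.

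**The case against.** The strongest case for leaving the rule alone has four parts.

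- **It errs conservatively.** A sensitive rule shortens duration of response, which is the safer direction in an uncontrolled trial, and a sum rule can miss or delay regrowth in one lesion. This stands. A reader might infer that the remedy is to replace the written rule and read all later scans on the sum whatever treatment was given. Step 6 shows that this would count relapsed and re-treated patients as continuing responders.
- **RECIST is named elsewhere, so the usual criteria may be intended.** Section 6.2.1 also refers to a Section 11 for evaluating measurable disease, but Section 11 of this document is the risk/benefit assessment. Whether another text supplies a sum or a minimum cannot be told from here. Even so, the only rule written out for these visits is the one in 7.1.1, so the places still need reconciling.
- **The size rests on assumptions.** Reading SD, number and size of lesions, and independence of errors are all assumed. At SD 5% the effect is 0.1 to 0.3 of a patient. This stands.
- **The examples are extreme.** The 1.4 mm case needs an entry-minimum lesion sitting at exactly a 30% response; the falling total needs lesions moving in opposite directions. They show what the wording permits, not what is likely.

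**Conclusion.** The point holds, at minor to moderate weight. The written rule is a sufficient condition for recurrence, has no sum and no absolute minimum, can be read two ways, and is not reconciled with Section 5.1.2 or Table 4. At an assumed SD of 7% and two lesions, the choice between any and all moves the false-call rate between 15.5% and 0.3%. Across SD 5 to 10% and one to three lesions, the any-lesion reading costs about 0.1 to 3.7 of roughly 7 responders, assuming the 40% target rate and that all responders reach the off-therapy visits.

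Three stronger readings are not supported:
- A reader might infer that the efficacy conclusion is at risk. It is not: the two-stage test uses PR+CR, and duration of response is descriptive.
- A reader might infer that one or two false events should be expected. That needs two or three lesions at SD 7%, or SD 10%, and the documents give neither.
- A reader might take it as stated that duration of response covers responders only and ends at this event. Both are reasonable inferences, but Section 7.1.3 defines no population, event or censoring rule for it, and says that every report will contain all patients.

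**What to change.** In 7.1.1 and 7.1.3:
1. State whether any or all target lesions must rise for the written event.
2. Pre-specify duration of response (and PFS, if it shares the event) on the sum of target-lesion diameters: 20% or more above the month-12 sum and above it by an absolute minimum, or a new lesion on scans already scheduled. Table 4 note E already provides for these: "All patient will have a whole body PET-CT and bone scan performed". The sponsor should set the minimum from its own reading variability.
3. Report this side by side with the 7.1.1 event. Treat symptoms, quality of life, SUV and cytokines as supportive.
4. Do not count a patient who resumed therapy as a continuing responder on later, on-therapy scans. Show the sum-based analysis twice: with resumption as an event and with censoring at resumption. Say in advance that the first returns close to the 7.1.1 rates if every call leads to resumption, and that the censoring in the second may be informative.
5. Reconcile 5.1.2, the Table 4 tumour-size row, note C-D and 7.1.1 on what counts as progression and how it bears on resumption; note C-D says that therapy will be resumed, 7.1.1 that it will be considered. No clinical rule is proposed here.

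The cost is rewording and a derivation from measurements already planned, with no new scans. The real price is later detection of regrowth confined to one lesion (step 5 of the working), which is why the written event should stay in the report.
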